5.3 Reporting procedures

All adverse events should be reported. Depending on the nature of the event the reporting procedures below should be followed. Any questions concerning adverse event reporting should be directed to the Chief Investigator in the first instance.

5.3.1 Non serious AEs

All such events, whether expected or not, should be recorded.

5.3.2 Serious AEs

An SAE form should be completed and faxed to the Chief Investigator within 24 hours. However, relapse and death due to non-obesity or diabetes related causes, and hospitalisations for elective treatment of a pre-existing condition do not need reporting as SAEs. All SAEs should be reported to the Charing Cross Hospital REC where in the opinion of the Chief Investigator, the event was:

- 'related', i.e. resulted from the administration of any of the research procedures; and
- 'unexpected', i.e. an event that is not listed in the protocol as an expected occurrence

Reports of related and unexpected SAEs should be submitted within 15 days of the Chief Investigator becoming aware of the event, using the NRES SAE form for non-IMP studies. Local investigators should report any SAEs as required by their Local Research Ethics Committee, Sponsor and/or Research & Development Office.

Contact details for reporting SAEs

[contact], attention [name] [name]

Please send SAE forms to: [name] [name], Imperial Weight Centre, [name].

[contact] (Mon to Fri 09.00 – 17.00)

6. Assessment and Follow Up

Assessment will take place through the use of dietary assessments, standardized meal tests and metabolic clamp tests. The dietary assessments will be completed once before and 1, 3, 6 and 12 months post all interventions. The meal tests will take place once before and 2 days, 7-30 days, 3 and 12 months after intervention. The metabolic study will be performed 4 times: at baseline, within 1-2 weeks of a low calorie diet and within 1-2 weeks after their weight loss treatment, whilst on the same liquid diet. The final study visit will take place 6-12 months after the weight loss treatment whilst patients are on their normal diet.

7. Statistics and Data Analysis

The groups will be allocated at random and thus the distribution of the data should be similar. A student's t-test will be used to compare the two groups for the primary and secondary end points. Descriptive statistics (proportions, mean, medians, standard errors and ranges) will be computed for all baseline variables with 95% CI using either exact binomial confidence intervals or t-confidence intervals for continuous outcomes (after appropriate transformation of the outcome to symmetry). All tests will be conducted at alpha=0.05. Previous studies investigating the effects of obesity surgery on macronutrient intake have recruited 50 patients per group and had power to detect significant differences. This type of study has never been performed with incretin pharmacotherapies and therefore will serve as a pilot for the investigation of the effects of this treatment intervention. The standardised meal study will have 80% statistical power to detect a difference of 5 pmol/L from the expected mean PYY level of 30 pmol/L when the usual standard deviation is 8 pmol/L, the sample size 20 subjects and the alpha error level 5%. This power calculation has been based on previous published results by the same group. Therefore 20 patients in each group are needed.

For the metabolic study, the endpoint is the minimum endogenous glucose production rate. Based on the HOMA-IR results from the only published study on patients having undergone the Endobarrier procedure, we will have a power of 81% at a p level of <0.05 if 6 patients complete the study. To allow for patients dropping out, a maximum of 10 patients will be enrolled to ensure 6 patients complete the study.

8. Regulatory Issues

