5.1 Definitions

Adverse Event (AE): any untoward medical occurrence in a patient or clinical study subject.

Serious Adverse Event (SAE): any untoward and unexpected medical occurrence or effect that:

- **Results in death**
- **Is life-threatening** – *refers to an event in which the subject was at risk of death at the time of the event; it does not refer to an event which hypothetically might have caused death if it were more severe*
- **Requires hospitalisation, or prolongation of existing inpatients' hospitalisation**
- **Results in persistent or significant disability or incapacity**
- **Is a congenital anomaly or birth defect**

Medical judgement should be exercised in deciding whether an AE is serious in other situations. Important AEs that are not immediately life-threatening or do not result in death or hospitalisation but may jeopardise the subject or may require intervention to prevent one of the other outcomes listed in the definition above, should also be considered serious.

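### Section 5.3.2 exempts a class of deaths from SAE reporting by disease cause, before the Chief Investigator judges relatedness and with no exception for deaths related to a research procedure

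*Combined protocol and SAP*

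**What the plan says.** Three places in section 5 bear on how a death is handled.

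- **5.1 Definitions.** An SAE is an untoward and unexpected occurrence or effect that meets one of the listed criteria. The first is "Results in death", with no restriction by cause.
- **5.3 Reporting procedures.** "All adverse events should be reported". The next sentence hands over to the subsections: "Depending on the nature of the event the reporting procedures below should be followed".
- **5.3.2 Serious AEs.** The section opens with the route: "An SAE form should be completed and faxed to the Chief Investigator within 24 hours". It then makes an exception for "relapse and death due to non-obesity or diabetes related causes" and, in the same sentence, "hospitalisations for elective treatment of a pre-existing condition do not need reporting as SAEs". The ethics committee rule follows: "All SAEs should be reported to the Charing Cross Hospital REC where in the opinion of the Chief Investigator, the event was" both related and unexpected. Related means that the event "resulted from the administration of any of the research procedures". Those reports are due within 15 days of the Chief Investigator learning of the event.

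Section 5.3.1 covers non-serious events and asks only that they be recorded.

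**The concern.** The exemption and the relatedness test ask different questions. The exemption asks which disease the patient died of. The committee rule asks whether a research procedure caused the event. A death caused by a research procedure need not be a disease death, so a filter on disease can remove the events that the relatedness test is there to find. The filter is applied first, by whoever labels the cause at the site.

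The research procedures are invasive. Section 3 describes five cannulated meal tests per patient in one subset, and up to four clamp visits in another, each with two cannulae, an insulin infusion and a tracer infusion. It continues the glucose infusion after the clamp because of the risk of hypoglycaemia. Section 4.2 lists no exclusion criteria. At stake is whether the Chief Investigator learns promptly of a death that the study itself may have caused.

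**Working it through.** No figure in the plan needs reproducing. The check is to follow a death through the text.

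1. **Is it an SAE?** Under 5.1, yes if it is untoward and unexpected. Cause plays no part.
2. **Must it go on the 24-hour form?** Under 5.3.2, not if it falls in the exempt class. That class is defined by disease cause only.
3. **Who judges relatedness, and on what?** The Chief Investigator, in a sentence about SAEs. The 24-hour form is the only defined route by which an event reaches that person.
4. **Is there another route?** The general sentence in 5.3 names no recipient and no deadline, and defers to the subsections. Section 5.3.1 is for non-serious events. An exempt death therefore has no defined path to the Chief Investigator.

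The exempt class can be read in two ways: (a) causes related to neither obesity nor diabetes; (b) non-obesity causes, and also diabetes-related causes. The examples below are illustrations; the documents do not list them as expected events.

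| Death, by cause label | SAE under 5.1 (if unexpected) | Form required, reading (a) | Form required, reading (b) |
|---|---|---|---|
| Complication of research cannulation or infusion, labelled neither obesity- nor diabetes-related | Yes | No | No |
| Glucose-related death around a clamp, labelled diabetes-related | Yes | Yes | No |
| Obesity-related | Yes | Yes | Yes |

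The first row is the gap, and it is there on both readings. The second row depends on the reading.

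**Exposure.** Section 3 gives eight groups of 50, so 8 × 50 = 400 patients. Meal tests involve 20 per group: 8 × 20 = 160. Clamps involve a different 10 to 20 per group: 8 × 10 = 80 to 8 × 20 = 160. If every group fills both subsets, 160 + 80 = 240 to 160 + 160 = 320 patients undergo research cannulation. If the maximum of 10 clamp patients in section 7 is a total for the whole study, the figure is 160 + 10 = 170. These are counts of patients exposed. The documents give no death rate, so no number of missed reports follows.

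**The case against.** The best defence is that the exemption lifts a reporting step and does not change what an SAE is. An unexpected death from a research procedure is still an SAE under 5.1, and the committee rule addresses related SAEs specifically, so it could be read as governing such a death. Section 5.3 also asks for all adverse events to be reported and sends questions to the Chief Investigator, and 5.3.2 tells local investigators to report SAEs as their local committee, sponsor or R&D office requires.

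Part of this stands. The text removes a duty to report and does not forbid reporting, and outside rules might catch the death. But the committee rule depends on the Chief Investigator's opinion, and that opinion needs a report that the exemption makes unnecessary. A site following an express exemption has little reason to ask. The local rules do not restore the 24-hour form or the relatedness judgement.

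The other side is also right on these inferences, which a reader might draw but the documents do not support:

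- *Diabetes-related deaths are plainly exempt.* That is reading (b), the less natural one in a study of both conditions. On reading (a), a hypoglycaemic death around a clamp may remain reportable.
- *Between-group counts of serious events will be biased.* None is planned. Section 3.1 lists dietary, appetite, hormonal and metabolic outcomes, and section 7 contains no safety analysis.
- *All 400 patients run the procedural risk equally.* Meal tests and clamps are confined to subsets.
- *Deleting the clause alone sends every death to the Chief Investigator.* It does not, because 5.1 still requires the event to be unexpected.

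A narrower edit is possible: keep the exemption for background deaths but not for deaths possibly related to a research procedure. It would leave the first judgement of relatedness with the site, which is the step at issue.

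**Conclusion.** The point holds, and 5.3.2 is wrong as written. It conflicts with the definition in 5.1 and the general duty in 5.3, and it screens deaths by disease cause ahead of the relatedness judgement with no exception for research-related deaths. The conclusion rests on two assumptions: that the specific exemption prevails over the general sentence in 5.3, as the deferral there indicates, and that no route to the Chief Investigator exists beyond those in section 5. If local, sponsor or R&D rules do require such reports, the practical gap narrows, but the contradiction remains.

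The size is a gap in oversight of an unknown and possibly very small number of deaths. No endpoint, estimate or planned comparison is affected. The term relapse is also undefined in this protocol, which suggests leftover wording but has no further consequence.

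**What to change.** In 5.3.2, delete the words "relapse and death due to non-obesity or diabetes related causes" together with the comma and conjunction that follow, so that only the exemption for elective hospitalisation remains. Add a sentence to 5.3.2 stating that any death, expected or not, goes on an SAE form to the Chief Investigator within 24 hours for a judgement of relatedness. The addition is needed so that the word *unexpected* in 5.1 does not reopen the gap.

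The committee filter for related and unexpected events stays as it is, so the committee's workload rises only if a death is judged to be both. The cost is one deleted clause, one added sentence and a few extra forms. Nothing in treatment, sample size or analysis changes.

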There is lack of prospective studies comparing the above obesity surgical procedures and their effects on food preferences, satiety, gut hormones, bile acids and hepatic glucose output. There is no data on incretin therapies and food preferences in humans [16].

2. Study Objectives

The objective of this study is to investigate the effects of obesity surgical procedures and incretin therapies on food preferences, satiety, gut hormones, bile acids and hepatic glucose output in overweight and obese patients.

3. Study Design

This is a prospective observational controlled trial. 400 overweight and/or obese patients (Body Mass Index $\geq 30 \text{ Kg/m}^2$) will be recruited from the Imperial College NHS Trust, Royal Surrey County Hospital, Musgrove Park Hospital, King's College Hospital and private obesity and/or Diabetes clinics and studied prospectively for 1 year. The study groups will be as follows (n=50 per group):

- Group A: Patients due to undergo gastric bypass
- Group B: Patients due to undergo gastric banding
- Group C: Patients due to undergo sleeve gastrectomy
- Group D: Patients due to undergo endoscopic EndobARRIER insertion
- Group E: Patients due to be commenced on Exenatide
- Group F: Patients due to be commenced on Liraglutide
- Group G (control): Patients due to be commenced on a lifestyle intervention programme
- Group H (control): Patients due to have non bariatric surgery (i.e. cholecystectomy) or an elective diagnostic endoscopy

As part of routine care these patients will be seen by a qualified doctor or dietitian/nutritionist/diabetes specialist nurse (DSN) before and after intervention. Patients in control group G and H will be asked to use a low calorie diet either as part of their routine care or for research purposes only. Patients will be asked to prospectively complete food diaries on three consecutive days which are representative of their usual dietary intake and have a dietary assessment. This assessment will take 30-45 minutes and will take the form of a short discussion of dietary habits and will include completion of eating behaviour questionnaires (assessing dietary/personality traits including restraint, disinhibition, external eating and emotional eating). The first dietary assessment will be completed before the intervention and at 1 month, 3 months, 6 months and 12 months after intervention. Total energy intake and macronutrient composition comparisons pre and post intervention will form the basis of our analysis.

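### Section 7 relies on random allocation to justify a plain between-group t-test, but section 3 forms all eight groups by the treatment patients are already due to have

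*Combined protocol and SAP*

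**What the plan says.** Section 7 (Statistics and Data Analysis) opens with "The groups will be allocated at random and thus the distribution of the data should be similar". The next sentence is "A student's t-test will be used to compare the two groups for the primary and secondary end points". Neither section 7 nor any other part of the document names a baseline, covariate or propensity adjustment. Baseline variables are to be summarised descriptively.

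Section 3 (Study Design) says "This is a prospective observational controlled trial". It lists Groups A to H, each defined by what the patient is already due to undergo, start or have. One example is "Group E: Patients due to be commenced on Exenatide". Another is control Group H: "Patients due to have non bariatric surgery (i.e. cholecystectomy) or an elective diagnostic endoscopy". Groups G and H will be asked to use a "low calorie diet either as part of their routine care or for research purposes only".

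Section 3 also says "Total energy intake and macronutrient composition comparisons pre and post intervention will form the basis of our analysis". Section 1.1 (Background) gives as part of the rationale: "There is lack of prospective studies comparing the above obesity surgical procedures and their effects on food preferences".

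**The concern.** The two sections give incompatible accounts of how the groups arise, and the analysis rests on the account that the design does not support. Section 7 moves from random allocation to similar distributions, and then to a test with no adjustment. Random allocation is the plan's only argument for comparability.

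Without it, a difference between groups in energy intake, macronutrient proportions or gut hormones may reflect who receives each treatment. The documents give grounds for expecting such differences in some groups. Section 1.1 introduces the incretin drugs as treatments for type 2 diabetes, and Group H is having a procedure for an unrelated reason. Section 4.2 lists no exclusion criteria that would narrow the contrast.

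Comparison between procedures is part of the stated rationale, so these contrasts are not incidental. A false statement of random allocation could also be carried into publications.

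**Working it through.** **Step 1: the text.** No arithmetic is needed for the main point.

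| Item | Section 3 | Section 7 |
|---|---|---|
| Design | Prospective, observational, controlled | Groups allocated at random |
| How groups form | Treatment or procedure already planned, A to H | Not described beyond that statement |
| Comparability | No argument given | Inferred from random allocation |
| Analysis | Pre/post comparisons as the basis | Student's t-test between groups |

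No section gives a randomisation method, ratio, stratification or concealment. That the t-test is unadjusted is inferred from the absence of any adjustment; the plan does not use the word.

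**Step 2: what else in the plan might close the gap.**
- Descriptive baseline statistics would reveal an imbalance but not correct it.
- The pilot label in section 7 tempers claims for Groups E and F, not for the surgical groups.
- The repeated liquid diet in the clamp study controls for diet within a patient, not for who enters each group.
- The low calorie diet in Groups G and H and the common BMI threshold of 30 narrow some differences. They do not make group membership random.

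**Step 3: illustrative size.** The plan has no figure for imbalance, so none can be reproduced. From the documents: n = 50 per group, n = 20 per group in the meal study, alpha 0.05. Assumed: two-sided tests, no true effect, baseline difference D = 0.3, 0.5 or 0.8 SD, within-group pre/post correlation r = 0.3, 0.5 or 0.7, and equal SDs before and after.

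Model A (groups regress to a common mean), standardised shifts:
- follow-up values: D × r
- change scores: D(1 − r)/√(2(1 − r))
- ANCOVA: 0

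Model B (groups keep stable, different means):
- follow-up values: D
- change scores: 0
- ANCOVA: D(1 − r), in outcome SDs

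The t-test rejection rates come from the noncentral t distribution with 2n − 2 df and noncentrality shift × √(n/2). The ANCOVA rates are simulated (20,000 runs per setting).

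Middle case, D = 0.5, r = 0.5, n = 50, so √(n/2) = 5:
- A, follow-up: shift 0.5 × 0.5 = 0.25; noncentrality 1.25; rejection 23.6%.
- A, change: shift 0.5 × 0.5/√1 = 0.25; rejection 23.6%.
- A, ANCOVA: 5.2%.
- B, follow-up: shift 0.5; noncentrality 2.5; rejection 69.7%.
- B, change: 5.0%.
- B, ANCOVA: shift 0.5 × 0.5 = 0.25 outcome SDs; rejection 28.6% (a separate run of 4,000 gave 27.7%).

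Range over all assumed D and r:

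| n per group | Model | Follow-up t-test | Change-score t-test | ANCOVA |
|---|---|---|---|---|
| 50 | A | 7.3% to 79.2% | 8.9% to 64.9% | about 5% |
| 50 | B | 31.8% to 97.7% | 5.0% | 9.5% to 76.4% |
| 20 | A | 5.9% to 40.8% | 6.5% to 30.8% | about 5% |
| 20 | B | 15.2% to 69.3% | 5.0% | 6.9% to 38.3% |

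The upper ends are extreme corners of the assumed range. The t-test on follow-up values is inflated under both models. Change scores and ANCOVA each hold the 5% level under one model only.

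**The case against.** The strongest reply is that the plan is mainly a within-patient study. Section 3 makes pre/post comparison the basis of the analysis, and section 7 does not say whether its t-test uses follow-up values or changes. The meal-study power points the same way: Φ(√20 × 5/8 − 1.96) = 79.8% matches the stated 80% as a one-sample or paired calculation, whereas 20 versus 20 gives about 51%. If changes are compared, model B gives 5%. This stands for within-patient results, and it means the largest figures above apply to only one reading of the t-test. It does not remove the problem. Section 7 explicitly compares groups, the design has two control groups, and comparing changes across groups can still be confounded (9% to 65% under model A at 50 per group).

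Second, D and r are assumptions and the resulting range is very wide. That is right: the figures show only that the bias could matter, and the case rests on the text.

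Third, the documents show differing indications for Groups E, F and H, not among the procedures A to D. That is also right. For A to D, confounding is a reasonable risk that the documents do not demonstrate.

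Fourth, the clamp study is very small. Section 7 expects 6 completers from at most 10 enrolled and ties its power statement to EndoBarrier patients, so a between-group clamp contrast is not clearly planned. This limits how much adjustment is feasible there.

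**Conclusion.** The concern holds. The random-allocation statement contradicts the design in section 3, and the inference of similar distributions falls with it. The between-group t-test is left without support for a causal reading. This must be fixed before analysis.

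The amount of bias cannot be known from the documents. Under the stated assumptions, at 50 per group in the middle case, a nominal 5% test on follow-up values rejects 24% or 70% of the time, depending on how the groups behave over time. Comparing changes gives 24% or 5%. No single model removes the bias under both patterns. The conclusion applies to between-group contrasts only and does not depend on these figures.

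**What to change.** Reconcile sections 3 and 7 as follows.

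1. Delete the random-allocation sentence and its inference. State that groups follow planned routine care, except that the low calorie diet in Groups G and H may be for research only.
2. State which analyses are within-patient and which are between-group.
3. For between-group contrasts, replace the plain t-test with a prespecified analysis using the pre-intervention value: baseline-adjusted ANCOVA or a mixed model, or change from baseline. Justify the choice and report the other as a sensitivity analysis. If clamp results are compared between groups, say which of the two pre-treatment clamps is the baseline.
4. Adjust for a few prespecified covariates where overlap and size allow. BMI, diabetes status, age, sex and site are reasonable candidates, but the final list is for the sponsor. In the substudies, use the baseline value and at most one or two covariates.
5. Report covariate overlap by group and describe results as adjusted associations.

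The cost is mainly wording and a little analysis, with no extra patients or visits. Age, sex and diabetes status are not listed as recorded and should be added to the baseline record if absent.

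Degrees of freedom for a pairwise comparison start at 2n − 2:
- 50 per group: 98 − 9 = 89 (baseline value, BMI, age, sex, diabetes status, and 4 for five site categories with private clinics pooled; more if they are separated).
- 20 per group: 38 − 2 or 3 = 36 or 35.
- 10 per group: 18 − 2 or 3 = 16 or 15.
- 6 clamp completers per group: 10 − 2 or 3 = 8 or 7.

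Overlap on diabetes status may be poor for Groups E and F. Unmeasured confounding by indication remains under any of these analyses, so conclusions must be more cautious.

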3.1 Study outcome measures

Primary Endpoint

The primary outcome measure will be total energy intake and dietary composition in terms macronutrient proportions (fat, saturated fat, carbohydrates, sugars, fibre, protein and salt).

Secondary outcomes

The secondary outcome measures will be the ratings of hunger and satiety, gut hormones, bile acid and lipid levels before and after a standardised meal. In the clamp studies, the outcome will also be hepatic glucose output and insulin resistance.

4. Participant Entry

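### Section 7's single two-group t-test does not fit an observational design with eight groups, eight unranked primary measures and four follow-up visits

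*Combined protocol and SAP*

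**What the plan says.** Section 7 (Statistics and Data Analysis) gives one rule for comparing groups: "A student's t-test will be used to compare the two groups for the primary and secondary end points". The sentence before it gives the premise: "The groups will be allocated at random and thus the distribution of the data should be similar". The error rate is set once for everything: "All tests will be conducted at alpha=0.05". Section 7 also describes the incretin work as a pilot.

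Section 3 (Study Design) calls the study observational and lists eight groups of 50, A to H. Each is defined by the treatment that is already planned; group A, for example, is "Patients due to undergo gastric bypass". Six groups are active (A to F) and two are labelled control. G is a lifestyle programme. H is non-bariatric surgery or diagnostic endoscopy. Section 3 adds: "Total energy intake and macronutrient composition comparisons pre and post intervention will form the basis of our analysis".

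Section 3.1 (Study outcome measures) makes total energy intake primary together with "macronutrient proportions (fat, saturated fat, carbohydrates, sugars, fibre, protein and salt", without ranking them. Section 6 (Assessment and Follow Up) fixes the timing: "The dietary assessments will be completed once before and 1, 3, 6 and 12 months post all interventions".

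**The concern.** The analysis rule describes a two-arm randomised comparison, which is not the study in Section 3. To apply it, an analyst must choose the two groups, the control, the measure, the visit and the scale (follow-up value, change between groups, or change within a group). The plan makes none of these choices, so they can be made after the data are seen, with each test at 0.05. Two competent analysts could report different primary results and both claim to have followed the plan. A reader could not tell a planned difference from one selected among many.

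The random-allocation premise also matters in its own right. It is the stated reason for expecting similar distributions, and Section 3 gives no basis for that expectation.

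**Working it through.** **Counts.** Eight groups give 8×7/2 = 28 pairs. Six active groups against two controls give 12 pairs, and against one control 6. Primary measures: 1 + 7 = 8. Follow-up visits: 4. One pair therefore carries 8×4 = 32 possible primary tests, and all pairs carry 28×32 = 896.

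**The plan's own figures.** The primary endpoint has no power figure to reproduce; 50 per group rests on precedent. The one checkable figure is the meal study's 80% (PYY difference 5 pmol/L, SD 8, n = 20, alpha 5%).
- One-sample or paired, normal approximation: Φ(5/(8/√20) − 1.96) = Φ(2.795 − 1.96) = 79.8%. This reproduces it, taking 8 as the SD of the differences if paired.
- Two groups of 20: Φ(5/(8√(2/20)) − 1.96) = Φ(1.976 − 1.96) = 50.7%. This does not.

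So the sizing fits a one-sample or pre/post comparison, while the stated test compares two groups. This shows that the choice of contrast is unsettled for the secondary outcomes too.

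**False positives, global null.** One measure, one visit, n = 50 per group, two-sided 0.05 (sidedness assumed). For k independent tests the chance of at least one false positive is 1 − 0.95^k. Pairs that share a group are correlated, so the relevant figure is the simulated one.

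| Family | k | If independent | Simulated |
|---|---|---|---|
| All pairs | 28 | 76% | 51% |
| A–F v both controls | 12 | 46% | 34% |
| A–F v one control | 6 | 26% | 20% |
| A–D v both controls (no incretin groups) | 8 | 34% | 27% |
| A–D v one control | 4 | 19% | 15–16% |

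**False positives when the expected shifts are real.** Section 1.1 expects lower intake, a smaller share of fat and sugars, and more fruit and vegetables. Assumed share model: fat, carbohydrate and protein shares Dirichlet with means 0.37, 0.45 and 0.18 and total 60; fibre is carbohydrate times a lognormal factor (SD 0.3); salt is independent. One visit:
- Fibre, protein and salt null: 15% for one pair, 72% over 12 pairs.
- Protein and salt null: 10% and 57%.
- Fibre, protein and salt null, with a common correlation of 0.9 assumed in place of the share model: 8% and 51%.

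More visits raise these figures. For one null measure in one pair over four visits, the chance is 10% to 16% (assumed correlation 0.9 to 0.5).

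**Cost of familywise control.** With n = 50 per group and 80% power, the detectable difference in one test at 0.05 is 0.566 SD (two-sample t). This is back-calculated, not a planned effect, and assumes no dropout. At that difference, Bonferroni over six contrasts (0.05/6 = 0.0083) gives 55.6% power. Restoring 80% takes about 78 per group.

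**Why the scale must be named.** With equal SDs, baseline-adjusted and change-score estimates differ by (1 − ρ)×D, where D is the baseline imbalance in SDs and ρ the baseline-to-follow-up correlation. For an assumed D = 1, the gap is 0.3 SD at ρ = 0.7 and 0.7 SD at ρ = 0.3.

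**The case against.** **The plan is not silent on contrasts.** A reader might infer that no comparator or contrast is named at all. The documents do not support that: Section 3 labels G and H as controls and gives a pre/post basis. The gap is narrower. The control for each active group, the post-intervention visit, and the link between pre/post change and a between-group t-test are all left open.

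**Part of the study is a pilot.** This stands for the incretin groups E and F, and the figures without them are lower (27% and 15–16%). It does not extend to groups A to D.

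**Adjustment across different treatments is optional.** This also stands. Each treatment can reasonably be treated as a separate question at 0.05, so unadjusted testing across treatments is not in itself an error. What is missing is a statement of that position, and a named measure, visit and contrast within each question.

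**Larger error rates are tempting but not supported.** One could suppose that only energy, fat and sugars change while the other five components stay null. Macronutrient shares that sum to one do not allow this. Under the share model the SDs are √(p(1−p)/61): 0.0618 for fat, 0.0637 for carbohydrate and 0.0492 for protein. A 0.57 SD fall in fat is 0.57×0.0618 = 0.0352. That must reappear as a rise of 0.0352/0.0637 = 0.55 SD in carbohydrate, 0.0352/0.0492 = 0.72 SD in protein, or a split. Only the cases with two or three null components are therefore used. Even the three-component case needs fibre's share of carbohydrate to offset the rise in carbohydrate.

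**Conclusion.** The point holds, and the rule is wrong as written rather than merely short of detail: a t-test of two randomly allocated groups cannot be applied to eight groups defined by planned treatment without choices the plan does not make. That conclusion rests on the text alone.

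Its size depends on assumptions. The global-null figures (51%, 34% and 20%, or 27% and 15–16% without E and F) assume 50 analysed per group, one measure and one visit. If the expected dietary shifts are real, the range is about 10% to 15% for one pair and 57% to 72% over 12 pairs under the assumed share model, and lower if the components are highly correlated. The documents give no correlations or effect sizes, so these figures show scale and do not predict the study's actual error rate.

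**What to change.** In Section 7:
1. Delete the statement that groups are randomly allocated.
2. Replace the t-test sentence with a between-group comparison of change from baseline that uses all eight groups, for example a repeated-measures model with group, visit, group × visit and baseline value, with the patient as the repeated unit. A t-test on change at a named visit between named groups would also remove the ambiguity, but uses less of the data.
3. State whether the baseline-adjusted or the change-score estimate is primary and report the other as a sensitivity analysis, since baselines may differ between non-randomised groups.
4. Name one primary measure and one primary visit (for example, total energy intake at 12 months), and the reference control, G or H, for each active group. Say what each contrast estimates: the two controls differ in kind, and both are asked to follow a low calorie diet.
5. Report the other components, visits and contrasts as estimates with 95% confidence intervals. Include procedure-versus-procedure contrasts, because the lack of such comparisons is part of the study's rationale.
6. Apply the same kind of model to the meal-test and clamp outcomes, which otherwise lose their only stated test.
7. State that E and F give pilot estimates. For the named primary contrasts, state either familywise control or separate questions at 0.05.

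**Cost.** This needs little extra analysis and no new data. If familywise control over six contrasts is chosen, power at 0.57 SD falls from 80% to about 56% with Bonferroni. Declaring separate questions avoids that loss. Neither choice removes confounding, because the groups are still defined by the treatment already due.
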